### 7.2.3 Management and Dose Modifications for Entinostat

If carboplatin and etoposide are held during induction, entinostat and atezolizumab will also be held.

If at any time atezolizumab is held for atezolizumab-related AEs, instruct the patient to continue to take entinostat and to notify the study team if the event gets worse. If the adverse event worsens, entinostat should then be held with atezolizumab until the adverse event improves as specified in the below management and dose modification tables for both drugs. Entinostat may also be held at the investigator discretion for severe or life-threatening events.

If entinostat is held in either induction or maintenance regimen, the other study drug(s) will also be held, unless the adverse event can clearly be attributed only to entinostat and not to the other study drugs, in which case carboplatin, etoposide, and atezolizumab may be given in accordance with the regimen at the time (i.e. induction or maintenance).

The following specific management and dose modifications will be made for adverse events thought to be at least possibly related to entinostat. Patients requiring a delay of  $> 3$  weeks will discontinue entinostat. Patients that require a dose reduction when already receiving dose level - 1 (2 mg PO, weekly, as per table above) will discontinue entinostat. It is recommended that investigators maximize treatment for nausea, vomiting and diarrhea. No specific entinostat dose reductions are required for anemia.

Neutropenia	Management/Next Dose for Entinostat
≤ Grade 1	No change in dose
Grade 2	Hold* until ≤ Grade 1. Resume at same dose level.
Grade 3	Hold until ≤ Grade 1. Resume at one dose level lower **
Grade 4	Discontinue entinostat ***
* For grade 2 neutropenia events occurring mid-cycle, treatment does not need to be held ** For grade 3 neutropenia events occurring mid-cycle, treatment should be held, but dose reduction not required upon resuming. If event persists to day 1 of next cycle, resuming at one dose level lower is required. *** Entinostat should be held for grade 4 events occurring mid-cycle and may resume at one dose level lower with GCSF support upon recovery to ≤ Grade 1.	
For neutropenia events occurring between days 2 and 21 of each cycle that improve by day 1 of subsequent cycle, dose reductions may be made at investigator discretion. GCSF support should be considered on subsequent cycles.	

Thrombocytopenia	Management/Next Dose for Entinostat
≤ Grade 1	No change in dose
Grade 2	Hold* until ≤ Grade 1. Resume at same dose level.
Grade 3	Hold until ≤ Grade 1. Resume at one dose level lower
Grade 4	Discontinue entinostat
* For grade 2 thrombocytopenia events occurring mid-cycle, treatment does not need to be held For thrombocytopenia events occurring between days 2 and 21 of each cycle, dose reductions at next cycle Day 1 may be made at investigator discretion, unless required as above	

Other non-hematologic AEs	Management/Next Dose for Entinostat
≤ Grade 2	No change in dose
Grade 3	Hold until ≤ grade 1. Resume at one dose level lower.
Grade 4	Discontinue entinostat

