## **1. OBJECTIVES**

### **1.1 Primary Objectives**

- 1.1.1 To determine the maximum tolerated dose (MTD) of entinostat in combination with carboplatin, etoposide, and atezolizumab.
- 1.1.2 To determine safety and tolerability of adding entinostat to carboplatin / etoposide / atezolizumab for extensive-stage small cell lung cancer (ES-SCLC).
- 1.1.3 To determine the feasibility of administering entinostat concomitantly with atezolizumab, carboplatin, and etoposide as determined by the proportion of patients who receive 3 or more cycles of the combination.

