### 7.1 Carboplatin and Etoposide

The following hematologic parameters must be met on **Day 1** of Cycles 1-4:

- Absolute neutrophil count (ANC)  $\geq 1500/\text{mm}^3$
- Hemoglobin  $\geq 8.0 \text{ g/dL}$
- Platelets  $\geq 100/\text{mm}^3$

If Day 1 parameters are not met and carboplatin and etoposide are held, all Day 1 treatments (carboplatin, etoposide, atezolizumab, and entinostat) will be delayed until parameters are met.

If delays  $>3$  weeks are required before carboplatin and etoposide can be resumed, induction will be discontinued. The patient may then initiate the maintenance regimen. Alternatively, the patient may discontinue all study treatment and standard of care atezolizumab may be continued per investigator discretion.

Supportive therapy with granulocyte colony stimulating factor (GCSF) in order to achieve Day 1 treatment parameters may be used per ASCO or NCCN guidelines.

Dose modifications for carboplatin and etoposide should be conducted per investigator discretion based on institutional standards and guidance from package inserts for each drug. In general, when dose modifications to entinostat are required (e.g., for hematologic adverse events), dose reductions for carboplatin and etoposide should strongly be considered unless the adverse event is clearly attributable to entinostat alone.

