## 7.3 Atezolizumab

### 7.3.1 General AE Management and Dose Modification Guidelines

There will be no dose reduction for atezolizumab in this study.

Atezolizumab will be given on day one of each cycle. If carboplatin and etoposide are held during induction, atezolizumab will also be held.

If entinostat is held during induction or maintenance, atezolizumab may continue if the adverse

event is deemed attributable only to entinostat, such as a hematologic toxicity.

If atezolizumab is held, carboplatin and etoposide may continue during induction. Entinostat may continue in either induction or maintenance regimen, unless the adverse event worsens and then entinostat should also be held. Entinostat may also be held at the investigator discretion for severe or life-threatening events.

Patients may temporarily suspend atezolizumab treatment for up to 84 days (12 weeks) beyond the scheduled date of delayed infusion if study drug-related toxicity requiring dose suspension is experienced. If atezolizumab is held because of AEs for >84 days beyond the scheduled date of infusion, the patient will be discontinued from atezolizumab and will be followed for safety and efficacy as specified in this protocol. If the AE resolves within 84 days and the patient is receiving corticosteroid therapy for the event, atezolizumab may be held for longer than 84 days (up to 4 weeks) in order to allow tapering of the steroid dose to  $\leq 10$  mg oral prednisone or equivalent.

Dose interruptions for reasons other than toxicity, such as surgical procedures, may be allowed. The acceptable length of interruption will be at the discretion of the study PI in consultation with CTEP.

Atezolizumab must be **permanently discontinued** if the patient experiences any of the following events, regardless of benefit:

- Grade 4 pneumonitis
- AST or ALT  $>5\times$ ULN or total bilirubin  $>3\times$ ULN
- Grade 4 diarrhea or colitis
- Grade 4 hypophysitis
- Any grade myasthenic syndrome/myasthenia gravis, Guillain-Barré or meningoencephalitis
- Grade 4 ocular inflammatory toxicity
- Grade 4 pancreatitis or any grade of recurrent pancreatitis
- Grade 4 rash
- Any grade myocarditis

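### Sections 7.2.3 and 7.3.1 conflict on holding carboplatin and etoposide in induction once a worsening atezolizumab-related event also puts entinostat on hold

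*Combined protocol and SAP*

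**What the plan says.** All places are in the combined protocol and SAP.

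- **Section 7.2.3, worsening event.** Entinostat continues at first when atezolizumab is held for an atezolizumab-related event. Then: "If the adverse event worsens, entinostat should then be held with atezolizumab until the adverse event improves".
- **Section 7.2.3, effect on the other drugs.** "If entinostat is held in either induction or maintenance regimen, the other study drug(s) will also be held". The section allows a single exception to this: "unless the adverse event can clearly be attributed only to entinostat and not to the other study drugs". Later in the section, patients who need a delay of more than 3 "weeks will discontinue entinostat"; that limit is stated for events at least possibly related to entinostat.
- **Section 7.3.1, atezolizumab held.** "If atezolizumab is held, carboplatin and etoposide may continue during induction". Entinostat may also go on, "unless the adverse event worsens and then entinostat should also be held". Atezolizumab may be suspended for up to 84 days.
- **Section 7.1.** If delays of more than 3 "weeks are required before carboplatin and etoposide can be resumed, induction will be discontinued". The patient may then start maintenance or leave study treatment.
- **Endpoints.** Objective 1.1.3 measures feasibility as the "proportion of patients who receive 3 or more cycles of the combination". Section 9.1 lists the number of cycles of the four-drug combination, at most 4, as a primary endpoint. Section 9.3 reports the feasibility proportion with a 90% confidence interval and sets no threshold.

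**The concern.** An investigator whose induction patient has a worsening atezolizumab-related event finds a mandatory hold of chemotherapy in one section and a permission to continue it in another. Through the 3-week limit in Section 7.1, the choice can decide whether a previously untreated patient keeps induction chemotherapy. That makes it a safety instruction as well as a drafting matter.

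There is also a measurement side. The count of four-drug cycles is a primary endpoint. If sites follow different sections, that count partly reflects which section was read and not only how well the regimen was tolerated.

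**Working it through.** The plan states no figure on this point, so there is nothing to reproduce. The check has two parts.

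**1. The passages side by side.** Setting: induction, Level 1, 2 or 3, atezolizumab held for an atezolizumab-related event that then worsens.

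- Entinostat: both sections now hold it. No conflict.
- Carboplatin and etoposide under 7.2.3: entinostat is on hold, so the other study drugs are held. The exception needs an event attributable to entinostat only. An atezolizumab-related event cannot meet it.
- Carboplatin and etoposide under 7.3.1: they may continue while atezolizumab is held. The same paragraph deals with worsening and adds only entinostat; it does not withdraw the chemotherapy permission.
- Level -1 gives no entinostat in induction, so the conflict cannot arise there.

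**2. Counting cycles under each reading.** Inputs: 21-day cycles, up to 4 induction cycles (Section 6.1), and the 3-week limits in 7.1 and 7.2.3. Assumptions: Cycle 1 is given in full, atezolizumab and entinostat go on hold together on Day 1 of the cycle shown, drugs resume once the hold ends, and nothing else stops treatment.

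- 7.2.3 reading: all four drugs are delayed together. A delay of 3 weeks or less still gives 4 cycles. A delay of more than 3 weeks ends induction at the cycles already given.
- 7.3.1 reading: chemotherapy stays on schedule (4 cycles). A cycle counts as four-drug only if its Day 1 falls outside the hold.

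| Hold | Chemotherapy cycles, 7.2.3 / 7.3.1 | Four-drug cycles, 7.2.3 / 7.3.1 | 3 or more four-drug cycles, 7.2.3 / 7.3.1 |
|---|---|---|---|
| One, 3 weeks or less | 4 / 4 | 4 / 3 | yes / yes |
| One, 4 weeks from C2D1 | 1 / 4 | 1 / 1 or 2 | no / no |
| One, 4 weeks from C3D1 | 2 / 4 | 2 / 2 | no / no |
| One, 4 weeks from C4D1 | 3 / 4 | 3 / 3 | yes / yes |
| Two, each 3 weeks or less | 4 / 4 | 4 / 2 | yes / no |

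The entry 1 or 2 depends on whether the 3-week entinostat limit in 7.2.3 is applied. With C2D1 at week 3, a 4-week hold runs to week 7 and covers C3D1 (week 6). C4D1 (week 9) is a four-drug cycle only if entinostat has not been stopped.

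If chemotherapy-only cycles were counted, the 4-week holds from C2D1 and C3D1 would give 1 or 2 cycles (fewer than 3) under 7.2.3 and 4 under 7.3.1. The documents contain no such counting rule, and none that excludes it in terms.

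**Weight of one patient whose feasibility result changes** (illustrative counts, exact Clopper-Pearson 90% intervals). At n = 12: 10/12 = 83.3% (56.2 to 97.0) against 9/12 = 75.0% (47.3 to 92.8). At n = 36: 30/36 = 83.3% (69.7 to 92.5) against 29/36 = 80.6% (66.6 to 90.5).

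**The case against.** The best defence is that 7.3.1 is permissive and 7.2.3 mandatory, so a site that holds everything complies with both. The two can also be read in sequence: 7.3.1 while only atezolizumab is held, 7.2.3 once entinostat is held too. The first part stands, and it would be too strong to say that the protocol issues two opposite commands. But a site that uses the permission in 7.3.1 after worsening breaches 7.2.3. The sequential reading has to be supplied by the reader, because 7.3.1 itself takes up worsening and leaves the chemotherapy permission in place.

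Two stronger readings are tempting and fail.

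- *That a patient who loses or keeps induction thereby fails or passes the feasibility endpoint.* Chemotherapy given while atezolizumab and entinostat are both held is not a cycle of the four-drug combination. On that count a single hold of more than 3 weeks gives the same result under both sections. The result changes only after repeated short holds, where 7.2.3 is the reading that favours 3 or more cycles, or if chemotherapy-only cycles were counted.
- *That any event lasting more than 21 days ends induction under 7.2.3 and 7.1.* Section 7.1 limits the chemotherapy delay, not the event. An event worsening on Day 8 has 14 days until the next Day 1, so it could last 14 + 21 = 35 days without exceeding the limit. After Day 3 of Cycle 4 no induction chemotherapy remains to be lost.

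Nor is it a contradiction in itself that 84 days exceeds 21 (84 / 21 = 4): the limits apply to different drugs. What is missing is a statement of which governs when both are running.

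**Conclusion.** The text is wrong as written. For a worsening atezolizumab-related event in induction at Levels 1 to 3, Section 7.2.3 requires carboplatin and etoposide to be held and Section 7.3.1 permits them to continue. When the resulting chemotherapy delay passes 3 weeks, the patient keeps 1 to 3 chemotherapy cycles under one reading and up to 4 under the other, depending on when the hold starts. The four-drug cycle count can differ by 1 after one short hold and by 2 after two. The effect on the 3-or-more-cycle proportion is confined to the conditions given above.

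These sizes are per affected patient and rest on the simplified hold pattern in the working. How many patients would be affected cannot be derived, because the documents give no rate for such events.

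A smaller defect sits alongside: 7.2.3 ties resumption to management tables for both drugs, but Section 7.3 has a list of permanent-discontinuation events and general guidance, and no atezolizumab table.

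**What to change.** - Reconcile Sections 7.1, 7.2.3 and 7.3.1 so that one rule, worded the same way in each, governs carboplatin and etoposide when entinostat is held because of a worsening atezolizumab-related event. Which clinical rule applies is for the sponsor's clinicians.
- State how the 3-week limit in 7.1 and the 84-day allowance in 7.3.1 work together in this case.
- Correct the pointer in 7.2.3 to an atezolizumab table.
- State in Section 9 whether a cycle with one or more drugs omitted counts toward the number of cycles received and the 3-or-more-cycle proportion.

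The cost is an amendment of wording in the treatment and statistical sections, with no added patients or procedures. A case report form code for the reason each dose was omitted would help the cycle count but is optional.

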## 7.3 Atezolizumab

### 7.3.1 General AE Management and Dose Modification Guidelines

There will be no dose reduction for atezolizumab in this study.

Atezolizumab will be given on day one of each cycle. If carboplatin and etoposide are held during induction, atezolizumab will also be held.

If entinostat is held during induction or maintenance, atezolizumab may continue if the adverse

event is deemed attributable only to entinostat, such as a hematologic toxicity.

If atezolizumab is held, carboplatin and etoposide may continue during induction. Entinostat may continue in either induction or maintenance regimen, unless the adverse event worsens and then entinostat should also be held. Entinostat may also be held at the investigator discretion for severe or life-threatening events.

Patients may temporarily suspend atezolizumab treatment for up to 84 days (12 weeks) beyond the scheduled date of delayed infusion if study drug-related toxicity requiring dose suspension is experienced. If atezolizumab is held because of AEs for >84 days beyond the scheduled date of infusion, the patient will be discontinued from atezolizumab and will be followed for safety and efficacy as specified in this protocol. If the AE resolves within 84 days and the patient is receiving corticosteroid therapy for the event, atezolizumab may be held for longer than 84 days (up to 4 weeks) in order to allow tapering of the steroid dose to  $\leq 10$  mg oral prednisone or equivalent.

Dose interruptions for reasons other than toxicity, such as surgical procedures, may be allowed. The acceptable length of interruption will be at the discretion of the study PI in consultation with CTEP.

Atezolizumab must be **permanently discontinued** if the patient experiences any of the following events, regardless of benefit:

- Grade 4 pneumonitis
- AST or ALT  $>5\times$ ULN or total bilirubin  $>3\times$ ULN
- Grade 4 diarrhea or colitis
- Grade 4 hypophysitis
- Any grade myasthenic syndrome/myasthenia gravis, Guillain-Barré or meningoencephalitis
- Grade 4 ocular inflammatory toxicity
- Grade 4 pancreatitis or any grade of recurrent pancreatitis
- Grade 4 rash
- Any grade myocarditis

Any toxicities associated or possibly associated with atezolizumab treatment should be managed according to standard medical practice. Additional tests, such as autoimmune serology or biopsies, may be used to determine a possible immunogenic etiology. Although most immune-related adverse events (irAEs) observed with immunomodulatory agents have been mild and self-limiting, such events should be recognized early and treated promptly to avoid potential major complications (Di Giacomo *et al.*, 2010). Discontinuation of atezolizumab may not have an immediate therapeutic effect, and there is no available antidote for atezolizumab. In severe cases, immune-related toxicities may be acutely managed with topical corticosteroids, systemic corticosteroids, or other immunosuppressive agents. The investigator should consider the benefit-risk balance prior to further administration of atezolizumab.

For detailed information regarding management of adverse events associated with atezolizumab, please refer to the most current version of the Atezolizumab Investigator's Brochure and the FDA product label.

The primary approach to grade 1 to 2 irAEs is supportive and symptomatic care with continued treatment with atezolizumab; for higher-grade irAEs, atezolizumab should be withheld and oral and/or parenteral steroids administered. Recurrent grade 2 irAEs may also mandate withholding atezolizumab or the use of steroids. Assessment of the benefit risk balance should be made by the investigator, with consideration of the totality of information as it pertains to the nature of the toxicity and the degree of clinical benefit a given patient may be experiencing prior to further administration of atezolizumab. Atezolizumab should be permanently discontinued in patients with life threatening irAEs.

Patients should be assessed clinically (including review of laboratory values) for toxicity prior to, during, and after each infusion. If unmanageable toxicity due to atezolizumab occurs at any time during the study, treatment with atezolizumab should be discontinued.

### 7.3.2 Systemic Immune Activation

Systemic immune activation is a rare condition characterized by an excessive immune response. Given the mechanism of action of atezolizumab, systemic immune activation is considered a potential risk when given in combination with other immunomodulating agents. Systemic immune activation should be included in the differential diagnosis for patients who, in the absence of an alternative etiology, develop a sepsis-like syndrome after administration of atezolizumab, and the initial evaluation should include the following:

- CBC with peripheral smear
- PT, PTT, fibrinogen, and D-dimer
- Ferritin
- Triglycerides
- AST, ALT, and total bilirubin
- LDH
- Complete neurologic and abdominal examination (assess for hepatosplenomegaly)

If systemic immune activation is still suspected after the initial evaluation, contact the Principal Investigator for additional recommendations.

## 8. PHARMACEUTICAL INFORMATION

A list of the adverse events and potential risks associated with the investigational or commercial agents administered in this study can be found in Section 10.1.

### 8.1 CTEP IND Agents

#### 8.1.1 Entinostat (NSC 706995)

Chemical name:	pyridine-3-ylmethyl N-[4-[(2-aminophenyl)carbamoyl]phenyl]methyl]carbamate	
Other names:	MS-27-275, MS-275, SNDX-275	
Classification:	Histone deacetylase inhibitor (HDACi)	
Molecular formula:	$C_{21}H_{20}N_4O_3$	M.W.: 376.41
Mode of Action:	Histone deacetylases (HDACs) are a family of enzymes that regulate chromatin remodeling and gene transcription via the dynamic process of acetylation and deacetylation of core histones. Entinostat inhibits histone deacetylases, changes chromatin configuration, and induces differentiation and apoptosis of cancer cells through an epigenetic mechanism.	
How Supplied:	Entinostat is supplied by the Syndax Pharmaceuticals, Inc. and distributed by the Pharmaceutical Management Branch, DCTD, NCI as 1 mg (either pink to light red or light pink to orange), or 5 mg (yellow) film-coated tablets (round-biconvex). Tablets are produced using the polymorph B form of the drug.	
	Each tablet also contains mannitol, sodium starch glycolate, hydroxypropyl cellulose, potassium bicarbonate, and magnesium stearate. The film coating is derived from an aqueous suspension consisting of one or more of the following ingredients (dependent on tablet strength): hypromellose, talc, polyethylene glycol, titanium dioxide, and ferric oxide pigments (red and yellow) as coloring. Tablets are provided in bottles of 12 tablets (1 mg) and 4 (5 mg).	
Storage:	Store the bottles at up to 25°C (77°F); excursions are permitted from 15°C to 30°C (59°F to 86°F).	
	If a storage temperature excursion is identified, promptly return Entinostat to the proper storage temperature and quarantine the supplies. Provide a detailed report of the excursion (including documentation of temperature monitoring and duration of the excursion) to [contact] for determination of suitability.	

**Stability:** Shelf life stability studies of the intact bottles are on-going.

**Route of Administration:** Oral, on an empty stomach, at least 2 hours after and 1 hour before a meal. Entinostat tablets should not be split, crushed, or chewed.

**Potential Drug Interactions:** *In vitro* studies show that entinostat is not metabolized by CYP enzymes, but rather by UGT 1A4 to form a glucuronide metabolite. Data from *in vitro* experiments showed that, while entinostat inhibited cytochrome P-450 (CYP) enzymes 2C8 and 3A4, the degree of the inhibition makes it unlikely that any *in vivo* systemic interactions would occur. Entinostat did not inhibit any tested UDP glucuronosyltransferase (UGT) enzymes. However, entinostat has the potential to induce CYP 1A2 and CYP 2C8. Finally, entinostat is a substrate for P-glycoprotein (P-gp) and breast cancer resistance protein (BCRP) transporters and does not inhibit either of these transport proteins.

Results of pharmacokinetic studies evaluating the effect of proton pump inhibitors on entinostat suggest that entinostat absorption is not affected by acid reducing agents.

